If infusion reaction: Tryptase and C3a u				X	X								
Premedication v		X	X										
Premedication reminder w		X											
Study Drug Administration				$X^{x}$									
Anti-PEG Antibody Testing (IgG, IgM)	X		X				X				X		X
Cytokines and CRP y			X	X	X								
Plasma PK Sampling z			X	X	X	X	X		X	X	X	X	X
Urine PK Sampling aa			X	X	X	X	X		X	X	X	X	X
Exploratory Biomarkers	X		$X^{bb}$		X	X	X	X	X	X	X		
Concomitant Medications	X						Continuo	us Monito	ring				
Review/Record AEs									_				
Study Completion											X		

Footnotes on following pages.

Note: The schedule of assessments for optional cohorts administered ALN-TTR02 once every 3 weeks is provided in Appendix 4.

- a Early termination procedures: if a patient withdraws prior to Day 56, then the Days 56 and 208 visits should be performed. If a patient is withdrawn/withdraws after Day 56 and prior to Day 208, then the Day 208 visit should be performed.
- b Interval medical history.
- c Focused physical examination (includes head/ears/eyes/nose/throat [HEENT], cardiovascular, respiratory, abdominal, and hepatic assessments). If the screening physical examination was performed within 72 hours of Day 0, then the pre-dose (Day 0) physical examination does not need to be repeated; however, the patient's weight will be obtained.
- d Weight measured on Day 0 and Day 28 will be used for calculating first and second dose, respectively.
- e Vital signs to include: blood pressure, pulse rate, oral body temperature, and respiratory rate. Parameters are to be measured in the supine position using an automated instrument after the patient has rested comfortably for 10 minutes.
- f Serial measures (vital signs and pulse oximetry) are to be measured within 30 minutes pre-dose; at the end of infusion (EOI); and 30 (±5) minutes; 1, 2, and 3 (±15 minutes) hours; 6, 12, and 18 (±30 minutes) hours; and 24 (+30 minutes) hours post-infusion.
- g Not needed if a normal echocardiogram has been obtained within the past 90 days.
- h Serial electrocardiograms (ECGs) will be collected in 3 replicates within 30 minutes pre-dose, EOI, and 30 (±5) minutes, 2 and 4 (±15 minutes) hours, and 24 (+30 minutes) hours post-infusion.

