#### 3.4 Pharmacokinetic Assessments

The PK evaluation will include plasma-concentration time profiles for siRNA ALN-18328 and the novel lipid components DLin-MC3-DMA and PEG2000-C-DMG. ALN-18328 concentration will be determined at specified time points post-dose. An assessment of plasma concentrations of free and encapsulated siRNA will be determined at specified time points. PEG2000-C-DMG and DLin-MC3-DMA will be determined at specified time points up to 180 days post-dose. Renal clearance (CLR) will be determined for ALN-18328 and DLin-MC3-DMA and/or its metabolites excreted in the urine.

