### 7.4 Pharmacokinetic Evaluations

### 7.4.1 Plasma Pharmacokinetics

The PK parameter estimates and dose proportionality profiles of ALN-TTR02 will be determined for ALN-TTR02 siRNA (ALN-18328) and liposome lipid components, DLin-MC3-DMA and PEG2000-C-DMG. The plasma concentration-time profiles for ALN-18328, DLin-MC3-DMA, and PEG2000-C-DMG will be determined and used in the PK analysis for all dose cohorts. In addition, free and encapsulated concentrations of siRNA will be determined in plasma at specified time points (see Table 1-1) for cohort 3 and onward, including any optional cohorts. The drug concentrations in the lower cohorts are expected to be undetectable for this analysis.

Blood sample collection times are included in the schedule of events (see Table 1-1). Plasma PK samples (siRNA and lipids) will be collected pre-dose (within 1 hour of planned dosing start), at EOI, and then 5, 10, and 30 minutes, and at 1, 2, 4, 6, 24, and 48 hours post infusion. Samples will also be collected on Days 7, 14, 21, 35, 42, 49, 56, 112, and 208 post infusion as well as at the ET visit (if applicable); for optional cohorts

dosed once every 3 weeks, samples will be collected on Days 7, 14, 21, 28, 35, 42, 56, 112, and 208 post infusion as well as at the ET visit (if applicable).

For the PK blood draws, the sampling windows are  $\pm 1$  minute for the 5- and 10- minute draws;  $\pm 2$  minutes for the 30-minute draws;  $\pm 5$  minutes for the 1-, 2-, 4-, and 6-hour draws; and  $\pm 120$  minutes for the 24- and 48-hour draws.

The EOI will usually occur at 60 minutes after the start of infusion, except in patients where the infusion has been prolonged. If the infusion is stopped, a PK blood sample will be taken when the infusion is stopped, and this sample will be treated as the EOI sample if the infusion is restarted. All remaining PK samples will be collected according to the schedule of assessments when the dose is completed (i.e., all post-infusion times are relative to the EOI, regardless of the duration of infusion).

In the event that a patient receives only 1 dose of study drug, plasma PK samples should be collected pre-dose (within 1 hour of planned dosing start), EOI, and then 5, 10, and 30 minutes; and 1, 2, 4, 6, 24 and 48 hours post infusion; and at Day 208.

Details of sample collection and processing for PK analyses will be included in a laboratory manual.

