### 9.2.1 Populations to be Analyzed

The following patient populations (i.e., analysis sets) may be evaluated and used for presentation of the data:

- Intent-to-Treat (ITT) Analysis Set: All patients who were enrolled and received study treatment. The ITT analysis set will be the primary set for the analysis of safety data.
- Per-Protocol (PP) Analysis Set: All patients in the ITT Analysis Set who had no major protocol violations.
- Pharmacokinetic (PK) Analysis Set: All patients in the ITT Analysis Set who have adequate data to determine a full PK profile.

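### The one-dose sentence in Protocol Section 7.4.1 names no plasma PK sample between 48 hours and Day 208, which contradicts the sampling schedule and, taken literally, cannot support the terminal parameters required for every treated patient

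*Protocol*

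**What the plan says.** **One-dose list.** Protocol Section 7.4.1 says: "In the event that a patient receives only 1 dose of study drug, plasma PK samples should be collected pre-dose". It then lists end of infusion, 5, 10 and 30 minutes, "and 1, 2, 4, 6, 24 and 48 hours post infusion; and at Day 208". It names nothing between 48 hours and Day 208.

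**General list.** Earlier in the same section, without reference to the number of doses: "Samples will also be collected on Days 7, 14, 21, 35, 42, 49, 56, 112, and 208 post infusion", plus a sample at any early-termination visit. Table 1-1 footnote z gives the same days, again with no one-dose exception.

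**Early termination.** Table 1-1 footnote a: "if a patient withdraws prior to Day 56, then the Days 56 and 208 visits should be performed". Sections 4.5.2 and 6.4 send a patient who leaves before Day 56 to the Day 56 assessments, and Section 6.3.8 includes a plasma PK sample among them. Section 4.5.2 also keeps scheduled follow-up in place after withdrawal for an adverse event.

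**What the samples are for.** Section 7.4.1 requires terminal half-life, lambda-z, AUC to infinity, CL, Vss and Vz for every patient who receives ALN-TTR02. Section 3.4 says that the lipid components "will be determined at specified time points up to 180 days post-dose"; the synopsis counts the 180 days from the second dose. The PK analysis set (Protocol Section 9.2.1, SAP Section 2.1) is: "All patients in the ITT Analysis Set who have adequate data to determine a full PK profile".

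**The concern.** The protocol gives two sampling instructions for the same patient. The one-dose sentence is the more specific, so a site could reasonably let it govern and skip the later draws. Samples not taken cannot be recovered.

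The documents provide several routes to a single dose: transaminases above the Section 5.7.1 threshold after dose 1, a dose-limiting toxicity (which under Section 5.7.4 halts all dosing pending committee review), failure of the eligibility recheck before dose 2 (Section 5.6), a missed dose, or withdrawal. Because a dose-limiting toxicity halts dosing generally, one event could leave more than one patient with a single dose.

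Plasma PK is a secondary objective and each cohort has three patients. At stake are those patients' terminal parameters, and possibly their place in the PK analysis set.

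**Working it through.** **1. The plan's own figure.** On the 4-week schedule, 208 − 28 = 180 days, which reproduces the synopsis figure for lipid follow-up after dose 2. On the 3-week schedule, 208 − 21 = 187 days.

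**2. Count of samples for a one-dose patient (4-week schedule).**

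| Source | From end of infusion to 48 h | After 48 h |
|---|---|---|
| Section 7.4.1, general list, and Table 1-1 footnote z | 10 | 9 (Days 7, 14, 21, 35, 42, 49, 56, 112, 208) |
| Section 7.4.1, one-dose sentence | 10 | 1 (Day 208) |

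Days omitted: 9 − 1 = 8. Gap: 208 − 2 = 206 days.

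**3. What the literal list can recover.** The documents give no half-life, phase split or quantification limit, so these are assumptions. Take C(t) = (1 − f)·2^(−t/a) + f·2^(−t/b), relative to end of infusion, with t in days, initial half-life a, terminal half-life b and terminal share f. The half-life is ln 2 divided by minus the slope of ln C on t.

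Example: a = 0.25 day (6 h), f = 5%, b = 30 days.

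- C(6 h) = 0.95 × 0.5 + 0.05 × 0.994 = 0.525, ln = −0.645
- C(24 h) = 0.95/16 + 0.05 × 0.977 = 0.108, ln = −2.223
- C(48 h) = 0.95/256 + 0.05 × 0.955 = 0.0515, ln = −2.967
- Least-squares slope over t = 0.25, 1 and 2: −1.295 per day
- Half-life: 0.693/1.295 = 0.54 day, against an assumed 30 days

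With a and f held and b varied from 3 to 60 days, the 6, 24 and 48 h points give 0.46 to 0.54 day. They barely respond to the quantity being estimated. Over a wider grid (a = 2 to 12 h, b = 5 to 40 days, f = 1% to 5%) they give about 0.3 to 1.0 day.

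**4. Whether Day 208 rescues it.** With a = 6 h and f = 5%, the Day 208 concentration as a fraction of end of infusion is 7 × 10⁻²³ for b = 3 days, 1.7 × 10⁻⁶ for 14, 4.1 × 10⁻⁴ for 30 and 4.5 × 10⁻³ for 60. If the quantification limit is assumed to be 0.01% to 0.1% of the end-of-infusion level, Day 208 is measurable only for half-lives of roughly 30 to 60 days or more. Where it is measurable, fitting 24 h, 48 h and Day 208 gives 27.5 days for a true 30 and 50.8 for a true 60.

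**5. What the general schedule recovers.** In the same noise-free illustration (a = 6 h, f = 5%), Days 7, 14 and 21 alone return the assumed half-life for b = 3, 7, 14, 30 and 60 days, with or without Day 56.

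**6. Two-dose patients.** After dose 2 they have six late samples: 7, 14, 21, 28, 84 and 180 days on the 4-week schedule. Using the Section 7.4.1 list for 3-week cohorts, the times are 7, 14, 21, 35, 91 and 187 days. At 28 days the dose 1 residue is 2^(−28/b) of the dose 2 terminal level: 0.2% for b = 3 days and 72% for b = 60. Under linear kinetics this residue raises the level but leaves the slope unchanged, and the fitted half-life equals the assumed one in every case.

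**The case against.** The strongest reply is that the protocol does not remove these samples. The one-dose sentence does not say that its list is exhaustive. The general list, footnote z and the visit instructions in Sections 6.3.4 and 6.3.6 to 6.3.9 still call for late plasma samples. On the 4-week schedule Days 7, 14 and 21 come before the dose 2 visit, so they will normally have been drawn before anyone knows that the second dose will not be given. This stands: the documents support a finding of contradiction and no more.

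Four stronger readings are tempting, and the documents do not support them.

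- **The study loses its terminal phase.** It does not. Two-dose patients have about 180 days of uninterrupted washout after dose 2.
- **AUC would be wrong by up to ten-fold.** Linear-trapezoid errors of that size arise in the simulation only at an assumed terminal half-life of 5 days. Day 208 would then be about 3 × 10⁻¹⁵ to 1.5 × 10⁻¹⁴ of the end-of-infusion level and could not be measured. Section 7.4.1 also allows compartmental analysis, and SAP Sections 1.1.2 and 4.4 place the PK methods in a separate plan and report.
- **One-dose patients are mostly toxicity cases.** No passage says so. Section 4.5.3 also covers missed doses and non-safety discontinuation.
- **These patients would certainly leave the PK analysis set.** Neither document defines adequate data or a full profile, so exclusion is a risk only.

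**Conclusion.** The point holds as an internal contradiction with a real consequence if it is resolved the wrong way. The one-dose sentence leaves out all eight scheduled days between 48 hours and Day 208 and conflicts with the general list, footnote z and the early-termination rule. A patient sampled strictly by that sentence would not yield reliable terminal half-life, lambda-z, AUC to infinity, CL or Vz, although the same section requires them. The loss specific to these patients is the long single-dose profile with no carry-over. A two-dose patient cannot supply it, because the dose 1 profile is cut off at Day 28 (or Day 21) and the later tail carries dose 1 residue.

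The size is illustrative: about 0.3 to 1 day estimated against an assumed 5 to 40 days, resting on biexponential decay and on half-lives and a phase split that the documents do not give. The number of one-dose patients cannot be known in advance; one in a cohort of three would be a third of that cohort, before any replacement under Section 4.5.3. The correction is worth making before sites apply the sentence.

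**What to change.** Delete the one-dose sentence from Section 7.4.1. Alternatively, replace it with a statement that a patient who receives only dose 1 keeps the late plasma PK samples of the applicable schedule (Table 1-1 footnote z, or Table 12-1 footnote z for 3-week cohorts) and any early-termination sample, all timed from dose 1. The PK analysis plan should derive that patient's terminal parameters from this single-dose profile. Referring to the schedule avoids creating a further day list that could drift out of step.

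Reconcile the two 3-week lists in the same edit. Section 7.4.1 includes Day 21 and omits Day 49; Table 12-1 footnote z does the reverse.

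The cost is one sentence and, relative to the literal list, up to eight extra tubes per one-dose patient on the 4-week schedule. All eight fall at visits where blood is already drawn for TTR under Section 7.3.1. A patient who has withdrawn might need added visits, for example at Day 112, which the early-termination rule does not require.

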### 7.4.2 Urine Pharmacokinetics

The PK profiles of ALN-18328 and DLin-MC3-DMA in urine will be evaluated to determine the CLR of ALN-18328 and DLin-MC3-DMA and/or its metabolites after dosing with ALN-TTR02. Urine sample collection times are included in the schedule of assessments (see Table 1-1 or Table 12-1 for optional cohorts dosed once every 3 weeks). Urine will be collected into suitable containers and kept refrigerated. Pre-dose samples will be collected within 1 hour of the planned dosing start. For the 0 to 6 hour collection, the patient should void at time 0 hours and discard the specimen. Details of sample collection and processing for PK analyses will be included in the laboratory manual.

The Central Laboratory for urine PK analysis is:

# 7.4.3 Banking of Serum for Future Studies

To explore the expression of hepatocyte derived proteins to further characterize the biological effects of siRNA, serum and plasma samples will be collected at selected time points (see Table 1-1).

Biological samples for biomarker research can be retained on behalf of Alnylam for a maximum of 15 years following the last patient's last visit in the study.

#### 8 REPORTING ADVERSE EVENTS

#### 8.1 **Adverse Event Definition**

An AE is any untoward medical occurrence in a patient or clinical investigational patient administered a pharmaceutical product and which does not necessarily have a causal relationship with this treatment.

An AE can therefore be any unfavorable and unintended sign (including an abnormal laboratory finding, for example), symptom, or disease temporally associated with the use of a medicinal product, whether or not considered related to the medicinal product.

#### 8.2 **Serious Adverse Event Definition**

An SAE is any untoward medical occurrence that at any dose:

- Results in death;
- Is life-threatening (an event which places the patient at immediate risk of death from the event as it occurred. It does not include an event that had it occurred in a more severe form might have caused death);
- Requires inpatient hospitalization or prolongation of existing hospitalization;
- Results in persistent or significant disability/incapacity;
- Is a congenital anomaly or birth defect;
- An important medical event that may not be immediately life-threatening or result in death or hospitalization but may jeopardize the patient or may require intervention to prevent one of the other outcomes listed in the definition above (e.g., such events include allergic bronchospasm, blood dyscrasias or convulsions, or the development of drug dependency or abuse).

#### 8.3 **Eliciting Adverse Event Information**

The patient should be asked about medically relevant changes in his/her health since the last visit. The patient should also be asked if he/she has been hospitalized, had any accidents, used any new medications, or changed concomitant medication routines (both prescription and OTC).

In addition to patient observations, AEs will be documented from any laboratory findings, physical examination findings, ECG changes or other documents.

### 8.4 Adverse Event Reporting

The Investigator is responsible for reporting all AEs that are observed or reported after the first dose of study drug regardless of their relationship to study drug through to Day 56.

Any medical condition that is present when a patient is screened and does not deteriorate should not be reported as an AE. However, if it does deteriorate at any time during the study, it should be reported as an AE.

All AEs must be fully recorded for 28 days from the start of infusion in the site's source records and in the patients' CRF, whether or not they are considered to be drug-related. Each AE should be described in detail: onset time and date, description of event, severity, relationship to investigational product, action taken, and outcome (including time and date of resolution, if applicable).

Adverse events should be followed for 28 days following the last dose of study drug or until recovery to the normal state has been achieved, whichever occurs first. In the event of a patient not returning to the clinical unit, the outcome of this event will be recorded as lost at follow up.

### 8.5 Adverse Event Reporting Period

As stated in Section 8.4, AEs will be assessed for 28 days following the last dose of study drug (Day 56 for patients receiving both doses of ALN-TTR02) or until recovery to the normal state has been achieved, whichever occurs first; all AEs that occur after the start of study drug administration on Day 0 (Baseline) must be reported in detail on the appropriate CRF page and followed to satisfactory resolution, or a period of 28 days after the last dose of study drug administration, whichever is shorter.

Serious AEs will be followed for 28 days following the last dose of study drug (Day 56 for patients receiving both doses of ALN-TTR02), or until satisfactory resolution, or until the SAE is considered by the Investigator to be chronic or the patient is stable, whichever occurs first.

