#### 5.10 Concomitant Medication / Treatment

Use of the following medications/treatments is prohibited during study participation:

- Any investigational agent other than ALN-TTR02, tafamidis, or diflunisal;
- Corticosteroids, other than those administered as premedications prior to the dose of ALN-TTR02, those used to treat an infusion reaction, or topical or inhaled corticosteroids.

Medications and treatments other than those specified above, including palliative and supportive care for disease-related symptoms, are permitted during the study.

Use of all concomitant medications during screening, pre-dose and post-dose up to Day 56/ET will be recorded on the patient's CRF. This will include all prescription

drugs, herbal preparations, over-the-counter (OTC) medications, vitamins, and minerals. Any changes in medications during the study will also be recorded on the CRF.

Any concomitant medication that is required for the patient's welfare may be given by the Investigator. However, it is the responsibility of the Investigator to ensure that details regarding the medication are recorded on the CRF, and coded using an internationally recognized and accepted coding dictionary.

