### 6.3.9 Day 112 (±10 days)

Patients will undergo the following procedures on the Day 112 study visit:

- Collect blood samples for the following tests:
  - Serum TTR protein, vitamin A, and RBP. Additionally, aliquots of serum samples will be taken and frozen, to permit testing of additional proteins related to ATTR.
  - o Day 112 PK sample.
- Collect urine for PK analysis.

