#### 6.3.10 Day 208 (±2 weeks)

Patients will undergo the following procedures on the Day 208 study visit:

- Collect blood samples for the following tests:
  - Serum TTR protein, vitamin A, and RBP. Additionally, aliquots of serum samples will be taken and frozen, to permit testing of additional proteins related to ATTR.
  - o Anti-PEG antibodies (IgG and IgM).
  - o Day 208 PK sample.
- Collect urine for PK analysis.

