#### 8.9 Outcome of Adverse Event

Outcome will be defined as:

- Resolved (with or without sequelae);
- Ongoing;
- Lost to follow up.

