### 8.11 Serious Adverse Event Reporting

An assessment of the seriousness of each AE will be made by the Investigator. Any AE and laboratory abnormality that meets the above seriousness criteria (Section 8.2) must be reported immediately to Alnylam, always within 24 hours from the time that site personnel first learn of the event. Every SAE must be documented by the Investigator on the Serious Adverse Event Report in addition to the documentation on the AE form in the CRF. All SAEs must be reported regardless of the relationship to study drug.

The initial report should include at least the following information:

- Patient's study number.
- Description and date of onset of the event.
- Criterion for serious.
- Preliminary assignment of causality to study drug.

If follow up is required, new information should be provided to Alnylam as it becomes available using the Serious Adverse Event Reporting form. Copies of discharge summaries, consultant reports, autopsy reports, and any other relevant documents may also be requested.

Appropriate remedial measures should be taken by the Investigator using his/her best medical judgment to treat the SAE. These measures and the patient's response to these measures should be recorded. All SAEs, regardless of relationship to study drug, will be followed by the Investigator until satisfactory resolution or the Investigator deems the SAE to be chronic or stable. Clinical, laboratory, and diagnostic measures should be employed by the Investigator as needed to adequately determine the etiology of the event.

The Investigator will be responsible for reporting all SAEs to the local IEC when required by national regulations.

Alnylam will be responsible for the reporting of all relevant events to the concerned regulatory authorities according to all applicable regulations.

In Europe, in accordance with the Directive 2001/20/EC, the Competent Authorities and the Ethics Committees in the concerned Member States will be notified of fatal and life-threatening Suspected Unexpected Serious Adverse Reactions (SUSARs) as soon as possible but no later than 7 calendar days after Alnylam has first knowledge of the minimum criteria for expedited reporting. Non fatal and non life-threatening SUSARs should be reported no later than 15 calendar days after Alnylam has first knowledge of them.

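### Protocol Section 8.5 lets follow-up of an open SAE stop 28 days after the last dose, while Section 8.11 sets no time limit

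*Protocol*

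**What the plan says.** Two sections of the protocol set the end of SAE follow-up.

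- **Section 8.5 (Adverse Event Reporting Period):** "Serious AEs will be followed for 28 days following the last dose of study drug (Day 56 for patients receiving both doses of ALN-TTR02"). The sentence goes on to offer resolution as an alternative end point and closes "until the SAE is considered by the Investigator to be chronic or the patient is stable, whichever occurs first".
- **Section 8.11 (Serious Adverse Event Reporting):** "All SAEs, regardless of relationship to study drug, will be followed by the Investigator until satisfactory resolution". The full condition is "until satisfactory resolution or the Investigator deems the SAE to be chronic or stable". No number of days appears.

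Section 4.5.2 adds a third duration. An AE that leads to withdrawal is to be followed through 56 days after the last dose.

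The SAP has no SAE follow-up rule that would settle the matter. SAP Section 4.5.2 specifies by-subject listings of deaths and SAEs.

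**The concern.** The two sections give different instructions for the same event. Under 8.5 an investigator may close an SAE at 28 days after the last dose even if it has neither resolved nor stabilised. Under 8.11 the investigator must continue.

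The 8.5 reading is one a site could reasonably adopt, because much of the protocol treats Day 56 as the finish. Section 6.3.8 labels it the end of study, Section 4.5 defines a completer by it, and Table 1-1 places study completion there. Section 5.10 stops routine medication recording at the same point: "Use of all concomitant medications during screening, pre-dose and post-dose up to Day 56/ET will be recorded". Section 6.6 allows entry to the extension study from 28 days after the last dose, which is the same day on which 8.5 lets follow-up end.

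What is at stake is the completeness of SAE outcomes. Section 8.9 allows three outcomes: "Resolved (with or without sequelae"), ongoing, or lost to follow-up. An SAE closed at the 8.5 limit would remain recorded as ongoing, whether it later resolved or worsened. With three patients per cohort and safety as the primary objective, one such record matters to the reader of the SAE listing, and it matters more to the patient.

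**Working it through.** **Inputs**

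- Last dose: Day 28 in the every-4-weeks regimen (Section 3.1) and Day 21 in the every-3-weeks regimen (Section 6).
- 8.5 limit: 28 days after the last dose.
- End of scheduled visits: Day 208, with one intervening visit on Day 112 (Sections 6.3.9 and 6.3.10).

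**The plan's own figure.** Day 28 + 28 = Day 56, which agrees with the day printed in 8.5. For the every-3-weeks cohorts, Day 21 + 28 = Day 49, so the printed Day 56 does not fit them. The contradiction does not depend on this.

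**The two rules side by side.** Let L be the day of the last dose, R the day of resolution, and C the day on which the SAE is judged chronic or stable.

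- Section 8.5: follow-up ends at min(L + 28, R, C).
- Section 8.11: follow-up ends at min(R, C).

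The rules differ only when min(R, C) falls after L + 28, that is, when the SAE is still open and neither chronic nor stable 28 days after the last dose. In that case 8.5 permits a stop and 8.11 forbids it.

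**Longest follow-up 8.5 requires.** For an unresolved, unstable SAE with onset on Day d in the every-4-weeks regimen, this is 56 − d:

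| Onset | Under 8.5 | Under 8.11 |
|---|---|---|
| Day 28 | 56 − 28 = 28 days | no limit |
| Day 42 | 56 − 42 = 14 days | no limit |
| Day 49 | 56 − 49 = 7 days | no limit |
| Day 55 | 56 − 55 = 1 day | no limit |

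The table takes dose 2 on Day 28 exactly. The +2-day window in Table 1-1 could move the limit to Day 58 and would add up to 2 days to each entry.

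**Withdrawal because of an SAE after dose 1 only (Day 0).** Three end points apply: Day 0 + 28 = Day 28 (8.5), Day 0 + 56 = Day 56 (4.5.2), and no limit (8.11).

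**Whether later visits close the gap.** From Day 56 to Day 208 is 208 − 56 = 152 days, with two scheduled visits. Section 6.3.9 opens its list "Patients will undergo the following procedures on the Day 112 study visit" and Section 6.3.10 opens "Patients will undergo the following procedures on the Day 208 study visit". Both lists contain only blood and urine sampling. The Day 56 list in Section 6.3.8, by contrast, includes documenting AEs. Table 1-1 shows AE review as continuous, but its text version does not show which visits that row spans, so it cannot be counted for or against the later visits.

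**The case against.** The strongest reply is that this is an editorial inconsistency with little practical reach.

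- **Section 8.11 is the SAE-specific section.** It covers 24-hour reporting, follow-up information as it arises, discharge and autopsy reports, and all SAEs. Section 8.5 is headed as a reporting period and sits with the general AE rules. A site would naturally apply 8.11, and doing so breaches neither section. This makes an early stop less likely. It does not reconcile the text, because 8.5 also speaks of following SAEs and makes the 28-day point binding by taking the earliest of its three end points.
- **Later visits have a stated safety purpose.** Section 3.1 says patients return for safety as well as PK and PD monitoring up to Day 208, and Section 6.5 allows unscheduled visits. This stands as mitigation, although the visit lists do not carry it through.
- **Other safeguards exist.** Section 4.5.1 requires consultation with the sponsor and notification of the Safety Review Committee. Section 4.5.2 keeps medically withdrawn patients under supervision. Section 7.2.7 provides for follow-up of unexplained abnormal laboratory results. Section 8.11 requires treatment of an SAE and the patient's response to be recorded, which weakens the medication-recording point. The early-withdrawal visits are a less certain safeguard: Table 1-1 footnote a asks for both Day 56 and Day 208 after withdrawal before Day 56, but Sections 4.5.2 and 6.4 ask only for the Day 56 assessments.
- **No decision rule or main table turns on it.** Escalation uses data through at least 96 hours after dosing, stopping is triggered by the occurrence of a DLT, and treatment-emergent status depends mainly on onset. This is correct and limits the severity.
- **The day counts restate the rule and do not estimate an effect.** This is also correct. The number of SAEs that would be affected cannot be known from the documents.

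None of these points removes the 28-day end point from 8.5.

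**Conclusion.** The concern holds. Section 8.5 contains a stated rule that permits follow-up to stop on an SAE that is unresolved and unstable, and this contradicts Section 8.11.

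Its reach is narrow: only SAEs still open, and neither chronic nor stable, 28 days after the last dose, at a site that works to 8.5. The number is likely small. Treatment-emergent incidence tables would be essentially unchanged; what could suffer is the recorded outcome of individual SAEs and the care of the patient concerned.

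The conclusion rests on the wording of the two sections and on the absence of any text giving one precedence. It does not rest on the unclear AE row of Table 1-1. It should be corrected at the next amendment, but it does not undermine the trial's analysis.

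**What to change.** Rewrite the SAE sentence in Section 8.5 so that it carries only the 8.11 end points, for example: *Follow-up of each SAE continues, without a day limit, to satisfactory resolution or until the Investigator judges the event chronic or the patient stable (see Section 8.11).* For SAEs this also removes the Day 56 reference that does not fit the every-3-weeks cohorts.

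Leave the 28-day rule and the Day 56 reference for ordinary AEs as they are, so that their follow-up does not become shorter than the reporting period in Section 8.4. Optionally, add to Sections 8.4 and 8.5 a pointer to the 56-day rule in Section 4.5.2 for AEs that lead to withdrawal.

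The cost is one sentence in an amendment and a few extra contacts for SAEs still open. The schedule of assessments does not change, and the treatment-emergent incidence tables are essentially unaffected.
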